2.1 Study Rationale

Although substantial improvements in diabetic retinopathy (DR) severity have been demonstrated in patients with NPDR following treatment with intravitreal VEGF inhibitors, aflibercept and ranibizumab, the use of intravitreal VEGF inhibitors for the treatment of NPDR is not considered standard of care (Flaxel 2020). NPDR is a slowly progressive asymptomatic condition that affects adults of a working age. Approved intravitreal VEGF inhibitors require a high treatment frequency for improving the severity of NPDR, and the burden of treatment is such that they are not considered standard of care treatment for NPDR in the absence of sight-threatening complications such as diabetic macular edema (DME) or proliferative diabetic retinopathy (PDR) (Flaxel 2020). There is a substantial medical need for a more durable therapeutic option that allows a lower treatment frequency that may be more suitable as a treatment for NPDR. KSI-301 has an extended ocular half-life (Section 2.2.3), which may result in a less frequent treatment regimen. In the ongoing Phase 1b portion of Study KSI-CL101, the safety and efficacy outcomes of participants with diabetic macular edema treated with KSI-301 5 mg have supported a prolonged (2 to 6 months) treatment interval. Study KS301P106 has been designed to evaluate extended treatment intervals of KSI-301 5 mg in participants with NPDR.

2.2 Background

2.2.1 Non-proliferative Diabetic Retinopathy

Diabetes mellitus (diabetes) is a chronic disease that exerts pathologic effects on multiple organ systems, including the microvasculature of the retina. All patients with diabetes are at risk of developing DR, a progressive condition that can result in severe vision loss. DR is a leading cause of vision loss in the working-age population and is classified in routine clinical practice according to the International Clinical Diabetic Retinopathy Disease Severity Scale in order of increasing severity (Flaxel 2020; Wu 2013), as follows:

- a) No apparent retinopathy (no diabetic fundus changes);
- b) Mild NPDR (few microaneurysms);
- c) Moderate NPDR (microaneurysms, intraretinal hemorrhages or venous beading that do not reach the severity of the reference photographs);
- d) Severe NPDR (fundus changes consistent with reference photographs); and

e) PDR (neovascularization of the disc, retina, iris, and angle; vitreous hemorrhage; or tractional retinal detachment).

In clinical trials, DR severity is described according to the well-characterized and validated ETDRS Diabetic Retinopathy Severity Scale (DRSS), which divides the above clinical scale into additional, more discrete categories based on standardized grading of retinal color fundus photographs.

Table 1:Abbreviated Summary of ETDRS Diabetic Retinopathy Severity
Scale for Individual Eyes

Level	Severity
10	DR absent
20	Micro-aneurisms only
35	Mild NPDR (HE, SE, and/or mild H)
43	Moderate NPDR (mild IRMA or moderate H)
47	Moderately severe NPDR (mild VB, moderate IRMA, or severe H)
53	Severe or very severe NPDR (moderate/severe VB, severe IRMA, and/or very severe H)
60	Scars of photocoagulation for PDR or severe NPDR (SPC)
61	Mild PDR
65	Moderate PDR
71, 75	High risk PDR

Abbreviations: H = Hemorrhage; HE = hard exudates; SE = soft exudates; IRMA = intraretinal microvascular abnormalities; VB = venous beading; DR = diabetic retinopathy; NPDR = non proliferative diabetic retinopathy; PDR = proliferative diabetic retinopathy.

Levels 35-53 require presence of microaneurysms in addition to specified abnormalities. The definition for each level assumes that the definition for any higher level is not met. Severities of abnormalities are defined in References 2 and 6.

Source: Adapted from: Supplementary Appendix from (ACCORD Study Group 2010).

According to the World Health Organization, the global prevalence of diabetes among adults over 18 years of age rose from 4.7% in 1980 to 8.5% in 2014. Concomitant with the rising prevalence of diabetes, the prevalence of diabetic retinopathy (DR) in patients with diabetes is also increasing. DR and its clinical sequelae are responsible for vision loss in as many as 2.6-3.7 million patients with diabetes worldwide (Cheloni 2019). The risk of DR increases with diabetes duration. The current global estimate of any DR prevalence among patients with diabetes is approximately 35% (Leasher 2016).

2.2.2 Vascular Endothelial Growth Factor

VEGF stimulates vascular endothelial cell growth and induces vascular permeability. Several mechanisms are involved in the regulation of VEGF gene expression, and hypoxia is a key factor that induces VEGF production. In addition, changes in glucose levels also contribute to VEGF expression and intraocular VEGF levels are elevated in patients with diabetes. In nonclinical

models, over-expression of VEGF leads to retinal pathologic events common in diabetic macular edema and DR. For example, retinal VEGF mRNA and protein levels were increased in rats with background diabetic retinopathy and correlated with the breakdown of the blood-retinal barrier. In addition, experimental injections of VEGF protein into non-human primate eyes recapitulate the DR phenotype including nonperfusion, microaneurysm formation, and preretinal neovascularization. (Aiello 1994; Durham 2011; Lu 1999; Tolentino 2002)

Among the VEGF family members, VEGF-A is the most strongly associated with angiogenesis and vascular leakage (Campochiaro 2015). Intravitreal VEGF-A inhibitors such as aflibercept and ranibizumab have been approved by regulatory authorities worldwide for use in multiple retinal vascular diseases. Phase 3 studies of intravitreal administration of ranibizumab and aflibercept in patients with DR demonstrated clinically significant improvements in DRSS and lower rates of DRSS worsening relative to sham control. (Bressler 2017; Stewart 2017; Wells 2015; Wells 2016)

2.2.3 Description of KSI-301

KSI-301 is an antibody biopolymer conjugate (ABC) developed using the Sponsor's proprietary ABC Platform[™] technology. The antibody portion of KSI-301 binds to VEGF-A with high affinity and inhibits the ability of VEGF-A to bind and activate its cognate receptors (VEGFR1 and VEGFR2) thereby acting as an anti-angiogenic and anti-permeability agent. The inert biopolymer portion is an ultra-hydrophilic phosphorylcholine polymer that significantly increases the overall molecular size of KSI-301, which in turn extends its ocular half-life by a factor **or and ocular concentrations at three months by a factor of or compared to** aflibercept. Due to the biophysical and biological properties of the ABC Platform on which it is built, KSI-301 is designed to have improved ocular durability, bioavailability, biocompatibility, and stability, and rapid systemic clearance. These properties make KSI-301 an ideal candidate for the management of retinal vascular diseases.

A detailed description of the chemistry, pharmacology, efficacy, and safety of KSI-301 is provided in the Investigator's Brochure.

2.3 Benefit/Risk Assessment

Detailed information about the known and expected benefits and risks and reasonably expected adverse events of KSI-301 may be found in the Investigator's Brochure (IB). A brief overview of known potential benefits and risks is provided in the subsections that follow.

2.3.1 Known Potential Benefits

KSI-301, an intravitreal VEGF inhibitor developed to treat NPDR, benefits from a welldocumented mechanism action in retinal vascular disease (Homayouni 2009). The efficacy and safety of commercially available intravitreal VEGF inhibitors in retinal vascular disease is also well-documented and established. Based on its molecular design and structure, *in vitro* and *in vivo* nonclinical testing, and clinical data to date, it is expected that the efficacy and safety of KSI-301 should be at least comparable to other anti-VEGF biologics such as ranibizumab or aflibercept.

Patients with NPDR are treated for underlying hyperglycemia, hyperlipidemia, and hypertension as clinically indicated. The adoption of approved anti-VEGF therapies for NPDR is constrained by the high treatment burden caused by their insufficient durability. Emerging efficacy data from the ongoing Phase 1b portion of Study KSI-CL-101 support KSI-301's extended ocular half-life and less frequent dose regimens. Thus, KSI-301 may provide clinically relevant benefits as an intravitreal therapy for NPDR.

2.3.2 Known Potential Risks

Potential risks of treatment with KSI-301 were identified based on therapeutic protein class effects, VEGF-inhibition class effects, the intravitreal route of administration, nonclinical findings, and Phase 1/1b clinical experience. In consideration of the Coronavirus disease (COVID-19) pandemic caused by the virus SARS-CoV-2 and the impact it may have on clinical trials, COVID-19 related risks to participants are also carefully considered. A summary of known potential risks associated with KSI-301 is provided in Table 2. Risks associated with COVID-19 are discussed below in Section 2.3.2.1.

Potential Risk of Clinical Significance	Summary of Data/ Rationale for Risk	Mitigation Strategy						
Study Intervention [KSI-301]								
Immunogenicity	As with all therapeutic proteins, there is a potential for an immune response in participants treated with KSI-301. Clinical experience with commercially available intravitreal VEGF inhibitors has shown that serious adverse events (SAEs) related to inflammatory reactions can occur. Additional details are provided in IB Section 5.4.2.1.	Participants will be monitored following the injection and instructed to report any symptoms suggestive of an immune response without delay to facilitate early diagnosis and treatment (Section 8.1.4). Participants with known hypersensitivity to intravitreal agents such as aflibercept or ranibizumab or any ingredient of KSI-301 are excluded from this study (Section 5.2.2).						
Arterial thromboembolic events (ATEs)	ATEs are defined as nonfatal stroke, nonfatal myocardial infarction, or vascular death (including deaths of unknown cause). There is a potential risk of ATEs following intravitreal use of VEGF inhibitors. Additional details are provided in IB Section 5.4.2.2.	Participants with recent history (6 months) of myocardial infarction, stroke, transient ischemic attack, acute congestive heart failure or any acute coronary event are excluded from this study (Section 5.2.2).						
Intraocular inflammation	Intraocular inflammation has been reported following treatment with intravitreal anti-VEGF medicines, including KSI-301. Additional details are provided in IB Section 5.4.2.3.	Participants will be monitored following the injection and instructed to report any symptoms suggestive of intraocular inflammation without delay to facilitate early diagnosis and treatment (Section 8.1.4). Participants with active ocular infection or inflammation in either eye (e.g., blepharitis, infectious conjunctivitis, keratitis, scleritis, endophthalmitis) are excluded from this study (Section 5.2.1). Participants with active intraocular inflammation will have study treatment interrupted (Section 7.1.1)						
Hypersensitivity	Hypersensitivity reactions may manifest as rash, pruritus, urticaria, severe anaphylactic/ anaphylactoid reactions, or severe intraocular inflammation. Additional details are provided in IB Section 5.4.2.4.	Participants with known hypersensitivity to intravitreal agents such as aflibercept or ranibizumab or any ingredient of KSI-301 are excluded from this study (Section 5.2.2).						

Table 2:Protocol KS301P106: Risk Assessment

Study Procedures	5	
Risks associated with the method of administration	These risks include endophthalmitis, increases in intraocular pressure, retinal detachment, retinal tear, traumatic cataract, and intraocular hemorrhage. Additional details are provided in IB Section 5.4.2.5.	Proper and aseptic injection technique when administering intravitreal injections will be used (Section 8.1.3). Participants will be monitored following the injection and instructed to report any symptoms suggestive of endophthalmitis or retinal detachment without delay to facilitate early diagnosis and treatment (Section 8.1.4). Intraocular pressure and the perfusion of the optic nerve head will also be monitored and managed (Section 8.1.4). Participants with active ocular infection or inflammation in either eye (e.g., blepharitis, infectious conjunctivitis, keratitis, scleritis, endophthalmitis) are excluded from this study (Section 5.2.1).
Exposure to SARS-CoV-2 virus	Section 2.3.2.1	Section 2.3.2.1

 Table 2:
 Protocol KS301P106: Risk Assessment (Cont'd)

2.3.2.1 Risks Associated with Exposure to the Virus SARS-CoV-2

In consideration of the Coronavirus disease (COVID-19) pandemic caused by the virus SARS-CoV-2 and the impact it may have on clinical trials, COVID-19 related risks to participants are carefully considered and will be documented on an ongoing basis. Studies suggest that intravitreal anti-VEGF treatment improved diabetic retinopathy and prevented disease progression in eyes with moderately severe to severe NPDR in patients without DME (Lim 2020). This trial affords participants the opportunity to potentially receive anti-VEGF therapy for their NPDR and potential sight-threatening complications of DME, PDR, and/or anterior segment neovascularization (ASNV) that develop during the study period. Measures that prioritize trial participant safety and data integrity have been developed in consideration of local guidelines.

As the pandemic situation develops, the Sponsor will reassess risks, which will be documented as part of the Sponsor's trial master file. In the event of escalation of the pandemic during this trial and local circumstances leading to a local change in risk assessment, additional measures may be implemented. In this case, an Investigator-driven risk assessment will be conducted and documented in the Investigator's site master file and communicated to the Sponsor.

2.3.3 Overall Benefit/Risk Conclusion

The potential benefits of treatment of NPDR with KSI-301 (longer treatment intervals) have been considered against both the risks associated with KSI-301 treatment and the COVID-19 pandemic. Participants in this study will be carefully monitored with special attention to known and potential risks and managed as appropriate. Exclusion criteria restrict enrollment of participants at higher risk, and routine monitoring and follow-up evaluations will be conducted for early detection of any adverse events (AEs), as noted in Section 8.3. Reassessment of the risks will continue as the COVID-19 situation develops and any changes to this approach will be documented accordingly.

In eyes with moderately severe to severe NPDR, intravitreal anti-VEGF treatment improved diabetic retinopathy and prevented disease progression (Lim 2020). Therefore, based upon the well-known, clinically demonstrated mechanism of action (Homayouni 2009); favorable nonclinical and Phase 1a/1b safety, tolerability and bioactivity data; and a study design that includes extensive monitoring and COVID-19 risk mitigation, the Sponsor considers that the potential risks of study participation are outweighed by the value of the information to be gained and further study is warranted.

3.0 OBJECTIVES AND ENDPOINTS

Objectives	Endpoints				
Primary					
To demonstrate that KSI-301 5 mg is superior to sham treatment, with respect to proportion of eyes improving ≥ 2 steps on DRSS from baseline at Week 48.	• The proportion of eyes improving ≥2 steps on DRSS from baseline at Week 48.				
Secondary					
To evaluate the effect of KSI-301 5 mg in decreasing the incidence and delaying the onset of vision- threatening complications of diabetes compared to above tractment	• Time to development of and proportion of eyes developing any of the following from baseline over time (individually and as a composite):				
sham treatment.	- PDR or ASNV;				
	 Vitreous hemorrhage or tractional retinal detachment believed to be due to proliferative diabetic retinopathy; or 				
	- DME.				
To evaluate the efficacy of KSI-301 5 mg compared to sham treatment.	 Proportion of eyes improving ≥2 or ≥3 steps on DRSS from baseline over time. 				
	 Proportion of eyes worsening ≥2 or ≥3 steps on DRSS from baseline over time. 				
To evaluate the safety and tolerability of KSI-301 5 mg compared to sham treatment.	• Incidence of ocular and systemic adverse events over time.				
To assess the systemic pharmacokinetics (exposure)	Systemic pharmacokinetic profile over time.				
and immunogenicity of KSI-301.	• Systemic anti-drug antibody status over time.				
Exploratory					
Additional exploratory endpoints will be further describe	d in the SAP.				

4.0 STUDY DESIGN

4.1 Overall Design

This is a Phase 3, prospective, randomized, double-masked, two-arm, multi-center study evaluating the efficacy and safety of repeated dosing of KSI-301 5 mg administered by intravitreal injections in participants with treatment-naïve NPDR.

The overall duration of the study is approximately 2 years (100 weeks) after the last participant is randomized to the study. Participant duration is defined as the date a signed written informed consent is provided through the last safety follow-up visit at Week 100; thus, participant duration is approximately 103 weeks and includes a screening period of up to 21 days (Days -21 to -1), a treatment period of approximately 92 weeks (Day 1 to Week 92), a safety/efficacy assessment at Week 96, and a final follow-up for safety assessments at Week 100

. The primary endpoint will be assessed at Week 48; secondary endpoints for efficacy will be assessed at Weeks 48 and 96.

A single eye per participant will be designated as the Study Eye. If both eyes are eligible to become the Study Eye, the eye with worse BCVA and/or worse DR severity at Screening will be selected as the Study Eye. If both eyes are eligible and have the same BCVA and/or DR severity or one eye has worse BCVA and the fellow eye has worse DR, the decision of which eye to select as the Study Eye will be made by the Investigator.

Participants will be randomly assigned (1:1) into one of two treatment arms:

- Group A: KSI-301 5 mg via intravitreal injection at Day 1, Week 8, Week 20, and every 24 weeks thereafter through Week 92.
- Group B: Sham injection at Day 1, Week 8, Week 20, and every 24 weeks thereafter through Week 92.

Randomization will be stratifie

Additional details of the randomization methods are described in the statistical analysis plan (SAP).

Participants who develop sight-threatening complications of DME, PDR, or ASNV in the study eye will be managed as outlined in Section 4.1.3.1.

4.1.1 Screening Period

Participants will provide written informed consent to participate in the study before completing any protocol-specified procedures or evaluations not considered to be part of the participant's standard care. After providing informed consent, participants will be evaluated for eligibility criteria during the screening period within 21 days before administration of study intervention(s).

Participants who do not meet eligibility criteria within the 21-day screening period will not be eligible for randomization and will be considered as screen-failed. However, a participant may be rescreened up to one additional time at the discretion of the Investigator and in consultation with the Sponsor (Section 5.4). Instructions for participants who meet all eligibility criteria at the Screening visit but do not meet the BCVA eligibility criteria when they return for the planned Day 1 visit are provided in Section 5.5.

When rescreening tests and procedures have been completed and results are available indicating the participant is eligible for study participation, the participant may be enrolled. When rescreening a participant, a new screening/enrollment number should be selected to ensure there is an audit trail for the screen failed participant.

4.1.2 Treatment Period

Participants in this study will be treated until Week 92 and will have additional efficacy and/or safety follow-up visits at Weeks 96 and 100, unless the Investigator decides to discontinue treatment, the Sponsor decides to terminate the study or until any of the reasons for withdrawal/ discontinuation provided in Section 7.2 are met.

4.1.3 Administration of Study Intervention

All participants will be treated starting on Day 1 through Week 92 according to their respective treatment group. The IRT will determine the dosing schedule and adjust it in consideration of missed visits, out of window visits, and missing data during a visit. If a visit is missed at which study treatment is scheduled to be administered, the missed dose should be made up as close to the originally scheduled visit as possible using an unscheduled visit. Adjustments to study intervention due to development of sight-threatening complications of DR are described in Section 4.1.3.1.

As shown in the dosing regimen schematic provided in Figure 1, participants will be treated according to the group to which they were randomized, as follows:

• Group A - KSI-301 5 mg via Intravitreal Injection:

Intravitreal KSI-301 5 mg injection will be administered on Day 1, Week 8, Week 20, Week 44, Week 68, and Week 92.

• Group B - Sham Injection:

To preserve study masking, sham injections are administered to Group B participants at visits in which KSI-301 is administered to Group A participants. Thus, sham injections will be administered on Day 1, Week 8, Week 20, Week 44, Week 68, and Week 92.

For all study participants, non-treatment study visits will occur on Week 32, Week 48, Week 56, Week 80, and Week 96. A final safety assessment will occur on Week 100 and will be done via telephone call for all participants, except in WOCBP, in which case a site visit is required to administer a pregnancy test.

		Year 1								PE				
Week		0	(4)	8	(12)	(16)	20	(24)	(28)	32	(36)	(40)	44	48
KSI-301 5 mg	Q24W													
Sham		0		0			0						0	
						Ĩ	Year 2						SE	SA
Week		(52)	56	(60)	(64)	68	(72)	(76)	80	(84)	(88)	92	96	100 ª
KSI-301 5 mg	Q24W													
Sham						0						0		

Figure 1: Protocol KS301P106: Masked Dosing Regimens by Week

Abbreviations: PE = primary endpoint; Q24W = once every 24 weeks; SA = safety assessment; SE = secondary endpoint.

^a Week 100 is a final safety assessment that will be done via telephone call for all participants, except in WOCBP, in which case a site visit is required for the safety assessment that includes a pregnancy test.

4.1.3.1 Sight-threatening Complications of Diabetic Retinopathy in the Study Eye

Definitions and Documentation of Sight-threatening Complications

In this study, sight-threatening complications of DR in the Study Eye include DME, PDR, and/or ASNV. The protocol definition of each sight-threatening complication in the Study Eye is provided in Table 3. The diagnosis of DME, PDR, and/or ASNV will be made by the masked Investigator.

Because the treatment schedule changes for participants who develop these complications (as described below), it is very important that the imaging and/or clinical documentation described in Table 3 is collected at the time of diagnosis. It is also very important that the color fundus photographs are submitted to the reading center, because the color fundus photographs from this visit will be used for DRSS endpoint assessment.

Table 3:	Protocol KS301P106: Sight-threatening Complications of Diabetic
	Retinopathy: Definitions and Required Documentation for Initial
	Diagnosis

Sight-threatening Complication	Definition	Required Documentation		
Diabetic Macular Edema (DME)	 CST of ≥320 microns on SD-OCT and at least 5-letter decrease in best corrected visual acuity from Day 1 due to DME (as assessed by the Investigator); or 	A fundus photograph and OCT (Section 8.1.6) of the Study Eye must be obtained prior to the first treatment of DME.		
	• CST of ≥350 microns on SD-OCT due to DME (as assessed by the Investigator).			
Proliferative Diabetic Retinopathy (PDR)	 Neovascularization of the disc (NVD) or neovascularization elsewhere (NVE); Vitreous hemorrhage; or Pre-retinal hemorrhage. 	PDR must be documented with fundus photography (Section 8.1.6) [and, optionally, fluorescein angiography (Section 8.1.8)] of the Study Eye prior to initiation of the first treatment of PDR.		
Anterior segment neovascularization (ASNV)	 Neovascularization of the iris (at least two cumulative clock hours); Neovascularization in the iridocorneal angle (as assessed clinically by gonioscopy); or Neovascular glaucoma. 	A fundus photograph of the Study Eye must be obtained prior to the first treatment of ASNV. ASNV must be documented by clinical exam. Anterior segment photographic documentation is preferred if possible, but not required.		

Treatment of Sight-threatening Complications of Diabetic Retinopathy

Participants who develop any of the sight-threatening complications of DR in the Study Eye that are described in Table 3 will be treated with open-label KSI-301 5 mg, irrespective of the treatment group that they were originally randomized into (KSI-301 5 mg or sham). The original treatment group randomization will remain masked throughout the study.

At the visit that a sight-threatening complication of DR (DME, PDR and/or ASNV) is diagnosed (i.e., the "Dx Visit"), treatment with open-label KSI-301 5 mg will be initiated. Starting at the Dx Visit, participants will no longer follow the study visits and assessments outlined in Section 1.3.1 (SoA-A), nor receive further masked treatments. Instead, they will follow the study visits and assessments outlined in Section 1.3.2 (SoA-B), which is specific to the participants who develop DME, PDR, and/or ASNV.

As shown in Figure 2, treatment of DME, PDR, and/or ASNV will consist of the following:

 Two doses of KSI-301 5 mg, given four weeks apart (+/- 7 days), followed by KSI-301 5 mg once every 12 weeks (Q12W; +/-14 days). Thus, the first dose shall occur during the study visit in which DME, PDR, and/or ASNV was diagnosed, and the second dose shall occur 4 weeks (+/- 7 days) later. Thereafter, subsequent doses shall occur Q12W (+/-14 days).

More frequent visits and more frequent treatments with KSI-301 5 mg and/or panretinal photocoagulation (PRP) are at the discretion of the Investigator if the sight-threatening complication(s) as described in Table 3 are still present. Treatment with KSI-301 5 mg may not be given more often than monthly $(28 \pm 7 \text{ days})$.

End of Study Considerations

For participants who develop any of the sight-threatening complications described in Table 3, the following shall be considered:

- Participants shall not receive any treatment with KSI-301 5 mg after Week 92 (i.e., 92 weeks after the day of randomization (Day 1)).
- Weeks 96 and 100 (relative to the day of randomization (Day 1)) include final safety assessments that are mandatory and shall also be conducted according to the SoA-B (Section 1.3.2).

Figure 2:Protocol KS301P106: Dosing Regimen by Week for All Participants
Who Develop Sight-threatening Complication(s) in the Study Eye

	Q4W (±	7 days)	C	12W (± 14 day	SE	SA	
Week	Dx Visit	Dx Visit + 4 Weeks	Dx Visit + 16 Weeks	Dx Visit + 28 Weeks		96	100 ^b
KSI-301 5 mg ^a							
KSI-301 5 mg via intravitreal injection							treatment Visit

- Abbreviations: Dx Visit = the first study visit where a sight-threatening complication of diabetic retinopathy (DME, PDR, and/or ASNV) is diagnosed; Q4W = once every 4 weeks; Q12W = once every 12 weeks; SA = safety assessment; SE = secondary endpoint.
- ^a All participants who develop sight-threatening complication(s) of DME, PDR, and/or ASNV will be treated with open-label KSI-301 5 mg, irrespective of the treatment group that they were originally randomized into. The participant's 'as randomized' treatment group will remain masked. Participants shall not receive any KSI-301 5 mg dose for sight-threatening complications after Week 92.
- ^b Week 100 is a final safety assessment that will be done via telephone call for all participants, except in WOCBP, in which case a site visit is required for the safety assessment that includes a pregnancy test.

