6.1 Study Intervention(s) Administered

Study interventions are summarized in Table 4. For full information regarding the administration of study intervention and the contents of the kit, refer to the Pharmacy Manual. The full instructions for administration of sham are also described in the Pharmacy Manual.

Table 4:Protocol KS301P106: Study Interventions

Group Name	А	В
Intervention Name	KSI-301 5 mg	Sham
Туре	Biological medicinal product	Sham
Dose Formulation	Sterile liquid for intravitreal injection in single-use vials	Empty vial
Unit Dose Strength(s)	mg/mL (based on antibody mass)	N/A
Dosage Level(s)	5 mg	N/A
Route of Administration	Intravitreal injection	Sham injection
Use	Experimental	Sham (to maintain study masking)
IMP and NIMP	IMP	NIMP
Sourcing	Provided centrally by the Sponsor	Provided centrally by the Sponsor
Storage	In the original packaging, as provided, until the time of use. Store at 2-8°C before use. Refer to Pharmacy Manual for additional instructions.	In the original packaging, as provided, until the time of use. Store at 2-8°C before use. Refer to Pharmacy Manual for additional instructions.
Packaging and Labeling	KSI-301 will be provided in vials that will be labeled as required per country requirement.	Sham will be provided in vials that will be labeled as required per country requirement.
Reconstitution and Handling	KSI-301 is an aqueous solution that is provided in vial and filled into a syringe by unmasked site personnel without reconstitution or dilution.	Sham is provided as empty glass vials, which will remain empty throughout the sham treatment procedure. A sham injection mimics an intravitreal injection. It involves pressing the blunt end of an empty syringe, without a needle, against an anesthetized eye.
Current/Former Name(s) or Alias(es)	N/A	N/A

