7.2.1 Proportion of Eyes Developing Any Sight-Threatening Complication

The first key secondary efficacy endpoint of interest is the proportion of eyes developing any of the following from baseline through Week 48:

- PDR or ASNV;
- Vitreous hemorrhage or tractional retinal detachment believed to be due to PDR; or
- DME.

The development of the above sight-threatening complications is tabulated from adverse events, procedures and eCRFs.

The following intercurrent events will be evaluated in this key secondary endpoint:

- Treatment misallocation at 1 or more study visits.

- Use of prohibited medications in the study eye.

-Premature discontinuation from study treatment due to study eye adverse events or due to lack of efficacy.

-Premature discontinuation from study treatment due to events unrelated to study treatment such as malignancies, systemic infections, trauma, or other systemic adverse events that are not treatment-related, including discontinuations due to COVID-19.

The same analysis method from the primary efficacy endpoint will be used for the first key secondary efficacy endpoint. See Section 7.1.2.

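### Protocol Table 3 counts vitreous or pre-retinal hemorrhage as PDR without asking the cause, so an injection-related bleed can enter two key secondaries despite the SAP's attribution wording

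*Protocol*

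**What the plan says.** Protocol 4.1.3.1, Table 3, gives three routes to PDR: neovascularization of the disc or elsewhere, and then "Vitreous hemorrhage; or Pre-retinal hemorrhage". Neither hemorrhage criterion mentions cause. The DME row of the same table does, for example "CST of ≥350 microns on SD-OCT due to DME (as assessed by the Investigator"). On who decides, the section says: "The diagnosis of DME, PDR, and/or ASNV will be made by the masked Investigator".

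SAP 3.1 sends the reader to Protocol Table 3 for the definition of each complication and offers no other definition of PDR. The composite in SAP 7.2.1 has PDR or ASNV as one component and, separately, "Vitreous hemorrhage or tractional retinal detachment believed to be due to PDR". Events are tabulated from adverse events, procedures and eCRFs. PDR alone is the third key secondary (SAP 7.2.3).

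Protocol 2.3.2, Table 2, says of the method of administration: "These risks include endophthalmitis, increases in intraocular pressure, retinal detachment, retinal tear, traumatic cataract, and intraocular hemorrhage". Protocol 6.1, Table 4, says of the sham: "It involves pressing the blunt end of an empty syringe, without a needle, against an anesthetized eye".

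**The concern.** Two definitions of the same event sit inside one endpoint. The looser one prevails, because an eye needs to meet only one component to count.

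The looseness is not neutral between arms. Bleeding caused by the needle is a recognized risk of giving KSI-301 and cannot follow the sham procedure. If such a bleed is recorded as PDR, a procedural complication is counted as disease progression, and during masked treatment that can happen in one arm only. The same bleed could also appear in the SAP 8.2 table of injection-procedure-related events, so the report could describe it in two incompatible ways.

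The composite is the first key secondary in a hierarchical family tested at 4.98% (SAP 7.2). If it fails, the later key secondary tests are closed.

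**Working it through.** **1. Follow one event through the definitions.** Take a vitreous hemorrhage that the Investigator does not believe is due to PDR.

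- Composite, hemorrhage component (SAP 7.2.1): not met, because attribution is required.
- Composite, PDR or ASNV component: met on the wording of Table 3.
- PDR alone (SAP 7.2.3): met.
- PDR or ASNV, and the time-to-event endpoints that include PDR (SAP Table 4): met.
- Hemorrhage or tractional detachment as a separate secondary (SAP Table 4): not met; the attribution works there.

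So in the composite the SAP qualifier has no effect for vitreous hemorrhage. It still works for tractional detachment, which Table 3 does not list. Pre-retinal hemorrhage appears only in Table 3, so no attribution applies to it anywhere.

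**2. Needle exposure.** Protocol 4.1.3: "Intravitreal KSI-301 5 mg injection will be administered on Day 1, Week 8, Week 20, Week 44, Week 68, and Week 92". Four of these fall before Week 48. With about 120 eyes per arm, 4 × 120 = 480 scheduled entries on KSI-301, and none on sham before a switch. A sham eye that switches to open-label KSI-301 for DME or ASNV then meets a needle. It already has a composite event, but a later bleed can still count for PDR alone, because the switch is not among the intercurrent events listed for that endpoint (SAP 7.2.1, applied by 7.2.3).

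**3. Ceiling on extra events.** The documents give no bleed rate. Let r be an assumed probability per injection that a bleed occurs and is counted as PDR. Expected eyes = 120 × [1 − (1 − r)^4].

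| r (assumed) | Expected events | P(no event) = (1 − r)^480 |
|---|---|---|
| 0.1% | 0.48 | 0.62 |
| 0.5% | 2.38 | 0.09 |

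**4. Effect on power.** No figure in the plan covers these endpoints. The stated power of at least 90% is for the primary endpoint, and its response rates are not visible. The event rates below are assumptions. Power = Φ[(d − z·SE0)/SE1], with 120 per arm, z = 1.9617 (two-sided 0.0498), pooled SE0 and unpooled SE1. Each extra event adds 1/120 = 0.83 percentage points to the KSI-301 rate.

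For 5% versus 15%: SE0 = √(0.10 × 0.90 × 2/120) = 0.03873; SE1 = √[(0.0475 + 0.1275)/120] = 0.03819; (0.10 − 1.9617 × 0.03873)/0.03819 = 0.629; power = 73.5%.

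| KSI-301 vs sham (assumed) | No extra event | One | Two |
|---|---|---|---|
| 5% vs 15% | 73.5% | 64.3% | 54.6% |
| 10% vs 30% | 97.6% | 96.2% | 94.2% |

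This is an unstratified approximation with no dropout; the planned test is a stratified CMH.

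**The case against.** The strongest reply is that diagnosing PDR is itself an attribution. Table 3 is headed as complications of diabetic retinopathy, a masked Investigator makes the diagnosis, and the clinical scale in Protocol 2.2.1 also lists vitreous hemorrhage under PDR without a qualifier. An obvious procedural bleed may well be set aside. That stands as a reason to expect few errors. It does not remove the conflict, because no text tells the Investigator to set such a bleed aside.

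The event counts are also ceilings. Unmasked staff do the immediate post-injection checks (Protocol 6.3.2). The next scheduled masked examinations come 8, 12, 12 and 4 weeks after the Day 1, Week 8, Week 20 and Week 44 injections. Absent an unscheduled visit, a bleed must persist until then and be called PDR. Missed doses, dropout and switches reduce the 480 entries. This objection stands in full.

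The bias is conservative for superiority, and a stricter count could delete true progression bleeds, mainly from the injected arm. That also stands, and it shapes the fix.

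A reader might infer that the error is possible only on KSI-301 throughout. The documents do not support that, because of the switched sham eyes described above. A reader might also infer a material loss of power. That depends on assumed rates: at 0.1% per injection no event is the likeliest outcome, and at higher event rates the loss is small.

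**Conclusion.** The inconsistency is real on the face of the documents and should be resolved before unmasking. It lets an injection-related bleed count as PDR in two key secondaries and the related PDR/ASNV and time-to-event endpoints. The exposure is one-sided during masked treatment, with a partial offset for PDR alone from sham eyes that switch.

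The direction is against KSI-301, so the definition does not threaten a false claim of superiority. The size is unknown: at most 0.5 to 2.4 events if 0.1% to 0.5% of injections led to a counted bleed. The effect on power ranges from minor to about 19 percentage points (73.5% to 54.6%) across the assumed scenarios, the larger loss needing two such events and low event rates.

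**What to change.** Add one rule to the SAP, before treatment codes are broken. For endpoint counting, vitreous or pre-retinal hemorrhage without neovascularization of the disc or elsewhere counts as PDR only if the masked Investigator attributes it to PDR. Apply it to the composite, PDR alone, PDR or ASNV, and the related time-to-event endpoints.

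Most of the information should already exist. The masked Investigator assesses causality (Protocol Synopsis), the relationship to the injection procedure or study intervention is part of that assessment (Protocol 10.3.3), and SAP 8.2 already tabulates procedure-related study-eye events. A hemorrhage recorded only as a complication, with no adverse event entry, would need a masked query.

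Report the unqualified Table 3 count as a sensitivity analysis. The rule relies on Investigator judgment, as the DME definition already does, and could exclude a true progression bleed; comparing the two counts would show whether that matters.

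The cost is one SAP sentence, one extra table and possibly a few queries. Table 3 also governs the move to open-label treatment, so the sponsor should reconcile the wording for that use as well; no treatment rule is proposed here.
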